12.1.3 Adverse Events Leading to Discontinuation

Adverse events leading to discontinuation of the study are those for which the answer to the AE CRF page's question of "Did the AE cause the subject to discontinue from the study?" is answered as "Yes."

12.1.4 Serious Adverse Events

Serious adverse events are those for which one or more of the following are indicated on the AE CRF page:

- Death
- Life-threatening
- Required or prolonged inpatient hospitalization
- Persistent or significant disability/incapacity
- Congenital anomaly
- Other medically important event

Subjects with "any serious adverse event" marked as "Yes" on CRF will be considered as serious AE even if one or more of the above specific events are not marked "Yes".

12.2 Clinical Laboratory Evaluation

Laboratory results will be classified based on the reference ranges provided by the central laboratory.

For quantitative laboratory parameters, observed and change from baseline measurements will be presented by time point using descriptive statistics. Categorical urinalysis parameters will only be presented in a listing. Laboratory parameters will be presented in SI units.

In the case of repeated laboratory values at the same visit, the last value collected will be used for the analysis.

The following laboratory parameters will be summarized:

- Hematology
 - White blood cell (WBC) count
 - Neutrophils
 - Lymphocytes
 - Eosinophils
 - Monocytes
 - Basophils
 - Hemoglobin
 - Hematocrit
 - Platelet count
 - Red blood cell (RBC) count
- Chemistry
 - Albumin
 - Alkaline phosphatase (AP)
 - Alanine aminotransferase (ALT)
 - Aspartate aminotransferase (AST)

- Blood urea nitrogen (BUN)
- Calcium
- Chloride
- Bicarbonate
- Creatinine
- Glucose
- Phosphorus
- Potassium
- Sodium
- Total bilirubin
- Total protein
- Total cholesterol
- High-density lipoprotein (HDL)
- Triglycerides
- Urinalysis
 - Protein
 - Glucose
 - Nitrite
 - Ketones
 - Blood
 - pH
 - Specific gravity
 - Leukocyte esterase
 - Microscopic bacteria
 - Red blood cells (RBC)
 - White blood cells (WBC)
 - Casts
 - Crystals
 - Cells

Microscopic examination of sediment will be performed only if the results of the urinalysis dipstick evaluation are positive, and will only be presented in a listing.

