#### 9.1.5 Clinical Laboratory

Samples of blood and urine will be collected for clinical laboratory tests during **Screening/Visit 1** and **EoS/Visit 2**. Tests will be conducted as designated below:

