#### 9.1.5.2 Abnormal and Clinically Significant Results

The Investigator must categorize all abnormal hematology, chemistry, and urinalysis laboratory values as either CS or NCS. Clinical significance is defined as any variation in laboratory parameters, which has medical consequences that result in an alteration in the subject's medical care. The Investigator will use the WHO Toxicity Criteria (see [Appendix 1](#)) as a guide when evaluating the clinical significance of all abnormal clinical laboratory results. In case of CS laboratory results, the Investigator will continue to monitor the subject with additional laboratory assessments until (1) values have reached normal range and/or baseline levels, or (2) the Investigator has judged that the abnormal values are not related to the administration of study drug or other protocol-specific procedures.

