#### **10.8.2 Physical Examinations, Vital Signs, ECG Parameters and Clinical Laboratory Test Values,**

By-subject listings of physical examinations, vital signs, ECG parameters and clinical laboratory data will include indications of values that are outside the reference ranges, and values that are clinically significant. Shift tables describing out-of-reference range shifts will be provided for vital signs, ECGs and clinical laboratory test results from the **Screening/Visit 1** to **EoS/Visit 2**, as appropriate by treatment arm and dose.

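### The SAP does not specify the laboratory and vital-sign shift tables promised in protocol 10.8.2, and its last-repeat rule for laboratory values has no post-dose exception

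*SAP*

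**What the plan says.** **Shift tables.** Protocol 10.8.2 commits to them: "Shift tables describing out-of-reference range shifts will be provided for vital signs, ECGs and clinical laboratory test results". They run from Screening/Visit 1 to EoS/Visit 2, as appropriate by arm and dose. For quantitative laboratory parameters, SAP 12.2 says "observed and change from baseline measurements will be presented by time point using descriptive statistics". SAP 12.3 plans the same kind of summary for blood pressure and heart rate. Neither section specifies a shift table, although SAP 12.4 and 12.5 keep shifts for ECG and physical examination. SAP 12.2 opens with "Laboratory results will be classified based on the reference ranges provided by the central laboratory" but names no table that uses the classes.

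**Changes from the protocol.** Protocol section 10 requires changes in analysis method, with their justification, to be described in the SAP. SAP 5.1 records other removals, such as two second-dose populations and the demographic tests, but not this one.

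**Repeat values.** SAP 12.2: "In the case of repeated laboratory values at the same visit, the last value collected will be used for the analysis". It does not separate baseline from post-dose samples. Protocol 9.1.5.2 says that after a clinically significant result "the Investigator will continue to monitor the subject with additional laboratory assessments until (1) values have reached normal range and/or baseline levels", or (2) until "the Investigator has judged that the abnormal values are not related to the administration of study drug" or to other protocol procedures. Protocol 9.1.5 schedules samples only at Visit 1 and Visit 2.

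**The concern.** SAP 3.4 names laboratory parameters and vital signs as safety endpoints, and each has one scheduled post-dose assessment. An uncommon effect on liver, kidney or blood pressure would show as a few subjects leaving the reference range in one arm and not in another. A shift table gives that count. A mean over several hundred subjects hardly moves, and a maximum shows one subject.

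The repeat rule could make this worse for laboratory data. Unless a clinically significant result is judged unrelated, re-testing stops only at a normal or baseline value. The results still thought possibly drug-related are therefore the ones most exposed to replacement, if their repeats count as belonging to Visit 2.

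**Working it through.** The plan states no figure on this point, so there is none to reproduce. The check is a comparison of texts, followed by a small illustration.

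**Step 1: which shift tables survive.**

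| Domain | Protocol 10.8.2 | SAP |
|---|---|---|
| Laboratory | shift table | values and change only (12.2) |
| Vital signs | shift table | values and change only (12.3) |
| ECG | shift table | shift kept (12.4) |

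Two of the three promised tables are not specified, and SAP 5.1 is silent on both. This part needs no assumption.

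**Step 2: what else would show an out-of-range value.**
- SAP 5 includes minimum and maximum among the descriptive statistics, so one extreme per group appears.
- SAP 12 lists all safety values, and protocol 10.8.2 has listings flag out-of-range and clinically significant values.
- Protocol 9.2.1 gives laboratory changes as an example of an adverse event when clinically relevant and followed by a medical intervention. SAP 12.1 counts events as treatment-emergent only up to 48 hours after a dose, while the Schedule of Assessments allows Visit 2 up to 7 days after treatment. An event dated to a later Visit 2 sample would enter the overall AE count but not the TEAE incidence tables.

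None of these gives a count of out-of-range results by arm.

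**Step 3: how the repeat rule acts.** At Visit 1 it agrees with SAP 5, which takes the latest pre-dose measurement as baseline. At Visit 2 it replaces an abnormal value only if (a) the result was judged clinically significant and re-tested, (b) the repeat is stored under Visit 2, and (c) the repeat has normalised. The documents do not settle (b): SAP 12.2 gives no rule for unscheduled or follow-up laboratory samples. The rule does not apply to vital signs.

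**Step 4: illustration.** The arm size of 570 is from protocol 10.1. The documents give no abnormality rates, so the rates, the 200 U/L rise and f are assumptions, where f is the fraction of clinically significant values replaced by a normalised repeat.

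Number remaining = 570 × rate × (1 - f):

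| Assumed rate | f = 0 | f = 0.5 | f = 1 |
|---|---|---|---|
| 0.5% | 2.85 | 1.43 | 0 |
| 1% | 5.7 | 2.85 | 0 |
| 2% | 11.4 | 5.7 | 0 |

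Rounding the 1% row to 6 subjects, 6(1-f) remain: 6, 3 or 0.

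Effect on the arm mean:
- one subject: 200 / 570 = 0.35 U/L
- six subjects: 6 × 200 / 570 = 2.11 U/L
- six subjects at f = 0.5: 3 × 200 / 570 = 1.05 U/L

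At f = 0 a shift table would show 6 of 570, provided all six began in range, whereas the planned table shows a change of about 2 U/L in the mean and a single maximum. At f = 1 that maximum is replaced too.

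**The case against.** The strongest reply concerns the repeat rule. It covers repeats at the same visit, which ordinarily means a duplicate or redraw. Follow-up until normalisation will usually fall on later dates, after the subject has finished the study, and nothing says those samples carry the Visit 2 label. A reader might infer that the SAP systematically erases clinically significant values; the documents support only a conditional risk. Values judged not clinically significant are not subject to the re-test rule, and monitoring may also stop on a judgement of unrelatedness while the value is still abnormal. This objection stands.

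A reader might also infer that shift counts are the only way to see an abnormal result, or that the tables would look clean whatever the drug did. Step 2 of the working rules that out: extremes, listings and, to a limited degree, adverse events remain. For vital signs no replacement rule exists, so extremes stay visible.

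Third, the omission may be incomplete specification rather than a decision. SAP 1 describes the SAP as updating and specifying the protocol's methods, SAP 12.2 classifies results by reference range, and protocol 10.8.2 qualifies its tables with as appropriate. That is plausible, and intent should not be alleged. The gap remains either way: the tables are not specified, and no reason is given.

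**Conclusion.** The point holds in two parts of different strength.

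The first rests on the text alone. Laboratory and vital-sign shift tables promised in the protocol are absent from the SAP without declaration or justification, and no planned table counts out-of-range shifts by arm.

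The second is conditional. The last-repeat rule can remove clinically significant post-dose laboratory values from the summaries, including the maximum, if follow-up samples are stored under Visit 2. Its size cannot be estimated from the documents. Under the assumed 6 of 570, anything from none (f = 0) to all six (f = 1) could be lost. Such values would leave the summaries but stay in the listings.

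The change is worth making before unblinding because listings and extremes do not provide a between-arm comparison of how many subjects went out of range.

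**What to change.** **SAP 12.2, repeats.** Keep the last pre-dose value as baseline. For Visit 2, analyse the first valid scheduled post-dose value, setting aside only samples that the laboratory reports as invalid. List later or unscheduled repeats as follow-up, and state how such samples are assigned to visits.

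**SAP 12.2 and 12.3, shift tables.** Specify the low/normal/high tables of protocol 10.8.2 from Visit 1 to Visit 2. Use central-laboratory ranges for laboratory tests. For vital signs, prespecify limits, because neither document defines any. SAP 12 presents these data by treatment sequence, which splits each active first-dose arm in two; add tables pooled by first-dose arm and keep those by sequence.

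**SAP 5.1.** If a table is to be left out after all, say so and give the reason, as protocol section 10 requires.

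**Cost.** SAP wording, standard programming and agreement on vital-sign limits; no new data. A few transient or spurious first values will be counted and need a footnote.

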12.3 Vital Signs

Observed and change from baseline values for vital sign measurements will be summarized for the following parameters:

- Systolic blood pressure (mmHg)
- Diastolic blood pressure (mmHg)
- Heart rate (bpm)

Baseline observations will also be presented for:

- Height (in)
- Weight (lb)
- BMI (kg/m²)

12.4 12-lead Electrocardiograms (ECGs)

The 12-lead Electrocardiogram (ECG) assessments will be performed at Visits 1 and 2. Observed and change from baseline summaries will be presented for quantitative measurements using descriptive statistics. Shifts in categorical ECG parameters will be summarized from baseline to Visit 2, and will

be classified as either:

- Normal
- Abnormal, Insignificant
- Abnormal, Significant

The following ECG parameters will be summarized.

- Heart rate
- PR interval
- QRS
- QT, uncorrected
- QTcB
- QTcF

Rhythm assessments will be presented in a listing.

QTcB is the QT interval corrected using Bazett's formula. It will be calculated as:

$$QT \text{ (msec)} / (RR \text{ (sec)})^{1/2}$$

QTcF is the QT interval corrected using Fridericia's formula. It will be calculated as:

$$QT \text{ (msec)} / (RR \text{ (sec)})^{1/3}$$

Changes from baseline to Visit 2 in QTcB and QTcF will also be summarized categorically, classified as follows:

- Less than 30 msec
- Greater than or equal to 30 msec and less than 60 msec
- Greater than or equal to 60 msec

12.5 Physical Examination

The shift in physical examination evaluations from baseline to Visit 2 will be summarized for each system for subjects who had a physical examination at Visit 2 as indicated by an adverse event.

- General appearance
- Skin
- Head, eyes, ears, nose, and throat (HEENT)
- Heart
- Lymph nodes
- Lungs
- Abdomen
- Extremities/joints
- Neurologic systems
- Mental status

For each system, the evaluation will be classified as:

- Normal
- Abnormal
- Not done

12.6 Columbia-Suicide Severity Rating Scale (C-SSRS)

At Visit 1, the C-SSRS will be used to assess suicidal ideation and behavior in the past six months. At Visit 2, the Since Last Visit version will be used to assess suicidal ideation and behavior since the last visit. Listings will present all C-SSRS data for subjects with at least one positive response to

either C-SSRS assessment.

13 RESOURCE UTILIZATION

A summary table will present counts and percentages of subjects who visited a cardiologist, or having procedures, hospitalizations, new treatments, or adjustments to treatments for any cardiovascular conditions or disease. Presented time points will be in the last six months prior to Visit 1 and since Visit 1 at the end of the study. Counts and percentages of subjects with emergency room or urgent care visits for migraines in the last three months prior to Visit 1 will be presented. This summary will be presented on the Safety population by treatment sequence.

Additional information regarding these visits or changes will be presented in a listing.

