**Resource utilization:**

- Any CV events in the 6 months prior to screening and/or related resource utilization such as visits to cardiologists, procedures, hospitalizations, new treatments or treatment adjustments for CV disease compared to on study Visit 1 through Visit 2.
- Any visits to an emergency room or physician's office for treatment of migraine in the 3 months prior to screening compared to on study Visit 1 through Visit 2, excluding study specific visits.
- Concomitant medications for the treatment of migraine and/or pain for 3 months prior to screening compared to concomitant medications for migraine and/or pain Visit 1 through Visit 2.
- Missed days of work and/or school.

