## 5.3 Additional Objectives

To explore the effect and time course of a second dose of lasmiditan 50 mg, of lasmiditan 100 mg and of lasmiditan 200 mg compared to placebo on relief of pain and MBS when used for rescue and for recurrence of migraine. To explore resource utilization during the study compared to pre-study in terms of cardiovascular events and in terms of migraine episodes.

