#### 9.1.1.3 Resource Utilization

During **Screening/Visit 1** subjects will be asked specifically about any CV events in the last 6 months and/or related resource utilization such as visits to cardiologists, procedures, hospitalizations, new treatments or treatment adjustments for CV disease. In addition information regarding any ER visits or visit to physician's office for migraine treatment will be recorded. At **EoS/Visit 2** the subject will again be asked about resource utilization during their time on study.

The subject will also be asked about the number of days missed from work and/or school during the migraine treated with study drug.

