3.5 Resource Utilization Endpoints

- Visits to a cardiologist, or any procedures, hospitalizations, new treatments, or adjustments to treatments for any cardiovascular conditions or disease
- Visits to an emergency room or urgent care for treatment of migraine

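### SAP section 13 sets six months of cardiovascular resource use before the study beside a much shorter on-study period as unadjusted percentages, and tabulates migraine emergency visits only before the study

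*SAP*

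**What the plan says.** Protocol section 5.3 sets an additional objective: "To explore resource utilization during the study compared to pre-study in terms of cardiovascular events and in terms of migraine episodes". For emergency room or office visits for migraine, the resource utilization list in the protocol synopsis defines the contrast as visits "in the 3 months prior to screening compared to on study Visit 1 through Visit 2, excluding study specific visits". The synopsis paragraph on resource utilization under statistical analysis sets Visit 1 information against Visit 2 information by treatment arm, and it covers both the cardiovascular items and the migraine visits. The on-study data are requested: under Protocol section 9.1.1.3, at Visit 2 "the subject will again be asked about resource utilization during their time on study".

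SAP section 13 turns this into one table on the Safety population, by treatment sequence. For cardiovascular use, "A summary table will present counts and percentages of subjects who visited a cardiologist" or had one of the other listed items, and "Presented time points will be in the last six months prior to Visit 1 and since Visit 1 at the end of the study". For migraine, subjects with "emergency room or urgent care visits for migraines in the last three months prior to Visit 1 will be presented". No on-study period is named for migraine. The section closes with "Additional information regarding these visits or changes will be presented in a listing".

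SAP section 3.5 keeps "Visits to an emergency room or urgent care for treatment of migraine" as an endpoint without naming a period. Physician's-office visits for migraine appear in neither SAP section. SAP section 5.1, which lists departures from the protocol's analysis, mentions none of this.

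**The concern.** There are two separate problems.

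First, the share of subjects with at least one event grows with the length of the period observed. A six-month percentage beside a percentage over a few weeks will differ even if nothing has changed. Protocol section 5.3 invites the reader to compare exactly these two figures. Protocol section 4 says the data will help confirm safety in patients with cardiovascular risk factors, so an apparent large drop in cardiovascular visits and procedures could be taken as reassurance when it only reflects the calendar.

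Second, the migraine half of the objective has a before figure and no during figure in the planned table. SAP section 13 gives two periods for cardiovascular use and one for migraine visits within the same paragraph. Protocol section 10 requires changes to the planned analysis methods to be described and justified in the SAP, and this one is not.

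**Working it through.** **Length of the on-study period.**
- SAP section 2.1 allows up to 7 days to the eligibility call, up to 56 days of treatment period and 7 days to Visit 2: 7 + 56 + 7 = 70 days = 10 weeks.
- The documents state about 11 weeks (protocol synopsis, Protocol section 5.5, SAP section 2.1). Using the 14 days for screening items in Protocol section 5.6.1 in place of the 7-day call window gives 14 + 56 + 7 = 77 days = 11 weeks. That this explains the extra week is an inference.
- Protocol section 5.5 also states about 12 weeks, with a 14-day window for Visit 2: 14 + 56 + 14 = 84 days = 12 weeks. The same section elsewhere gives 7 days and 11 weeks, so these passages need to be reconciled.
- Typical duration is not stated. Inclusion criterion 6 requires 3 to 8 attacks a month, a mean gap of 30/8 = 3.75 to 30/3 = 10 days. With both 7-day windows used in full, time on study is (7 + 3.75 + 7)/7 = 2.5 weeks to (7 + 10 + 7)/7 = 3.4 weeks. This is an inference. The table uses the Safety population, which contains dosed subjects only, so those who waited eight weeks without treating an attack are not in it.

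**Effect of unequal periods on cardiovascular use.** The documents give no event rates, so assume 2%, 5% or 10% of subjects have an event in six months, at a constant rate that does not change on study. Six months is 365.25/2/7 = 26.09 weeks. With p the six-month proportion, the weekly rate is r = -ln(1 - p)/26.09, and the proportion with an event in T weeks is 1 - exp(-rT).

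Example: p = 5% gives r = 0.05129/26.09 = 0.001966. At T = 10, 1 - exp(-0.01966) = 1.95%, and the apparent fall is 1 - 1.95/5 = 61%.

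| Weeks on study | Share of 26.09 weeks | On-study %, for 2% / 5% / 10% before | Apparent fall |
|---|---|---|---|
| 3 | 0.115 | 0.23 / 0.59 / 1.20 | 88% |
| 6 | 0.230 | 0.46 / 1.17 / 2.39 | 76-77% |
| 10 | 0.383 | 0.77 / 1.95 / 3.96 | 60-61% |
| 11 | 0.422 | 0.85 / 2.14 / 4.35 | 57-58% |
| 12 | 0.460 | 0.92 / 2.33 / 4.73 | 53-54% |

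The relative fall hardly depends on the assumed starting percentage. It is set by the ratio of the two period lengths.

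**Check that person-time removes the artefact.** With p = 10%, the pre-study rate is -ln(0.90)/0.5 year = 21.1 per 100 person-years. On study at 10 weeks it is -ln(1 - 0.0396)/(70/365.25 year) = 21.1, and at 2 weeks (0.80% of subjects) it is again 21.1. If only yes/no is recorded and subjects with an event are divided by total person-months, agreement is close but not exact: 10/6 = 1.67 per 100 person-months before, against 3.96/2.30 = 1.72 at 10 weeks (70/30.44 = 2.30 months).

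**Migraine visits.** This is a comparison of texts. The protocol synopsis asks for three months before against Visit 1 through Visit 2, for emergency room and office visits. SAP section 13 tabulates three months before only, for emergency room and urgent care visits. The on-study column and the office visits are missing, and SAP section 5.1 is silent on both.

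**The case against.** The strongest reply is that no biased estimate is planned. SAP section 13 specifies counts and percentages at two labelled periods, with no change score, ratio, test or interval, and Protocol section 10.9 promises only listings and descriptive statistics. A careful reader would see that the periods differ. This stands in part: the defect is in what the table invites the reader to conclude, not in a test. But before versus during is the comparison the protocol names, and the planned table gives no time on study from which to correct it.

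Several stronger readings are tempting and are not supported:
- A reader might infer that treatment comparisons are distorted. They are not: arms are randomized and share the same visit windows, and the artefact falls on placebo as well.
- A reader might take the six-month mismatch to cover all resource use. It applies to cardiovascular use only; the migraine look-back is three months.
- A reader might compute an apparent fall for migraine visits too. That would describe an on-study column the SAP does not plan.
- A reader might describe the objective as within-subject. The protocol asks for a before-versus-during comparison, summarized by arm.
- A reader might conclude that on-study migraine visits are lost. They are asked about at Visit 2, may appear in the listing, and remain an endpoint in SAP section 3.5. What is missing is the summary.

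It is also fair to say that person-time does not make the contrast clean. Protocol section 9.1.1 has the investigator exclude subjects with ongoing significant major organ disease, and Protocol sections 7.3.1 and 7.4 restrict migraine treatment on study, so the periods differ in more than length. Nor do the documents show whether the case report form records counts or only yes/no, or captures on-study office visits.

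**Conclusion.** Both parts hold, within limits. For cardiovascular use, the table as planned would show unchanged use as an apparent fall of more than half even at the longest stated duration: about 53-54% at 12 weeks, 57-58% at 11, 61% at 10 and 88% at 3, in every arm. These figures assume a constant rate and six-month percentages of 2% to 10%. The 3-week case rests on an inference from attack frequency. For migraine visits, the during-study half of the stated comparison is not tabulated, office visits are dropped, and the departure is not declared.

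The consequence is confined to a descriptive, exploratory contrast under an additional objective. The primary and key secondary tests, the significance level, the sample size and randomized comparisons on study are unaffected. The point is still worth correcting before the table is produced, because the layout is misleading as written and the repair is small.

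**What to change.** Revise SAP section 13 and its table shell as follows.
- Add an on-study column (Visit 1 to Visit 2) for migraine emergency or urgent care visits, and for office visits where captured, excluding study visits.
- Report each item in both periods per unit of person-time, using each subject's own Visit 1 to Visit 2 time on study, and six months (cardiovascular) or three months (migraine) before. If only yes/no is recorded, give subjects with an event per person-month.
- State the window lengths and the median on-study time in the table.
- Record in SAP section 5.1 any remaining departure from the protocol, such as omitting office visits if they were not captured.

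The cost is some SAP wording and one revised table shell, with no change to visits or trial conduct. How fully counts and office visits can be reported depends on the case report form, which is not among the documents. The contrast should still be labelled descriptive.

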#### Resource Utilization:

Resource utilization such as visits to cardiologists, procedures, hospitalizations, new treatments or treatment adjustments for CV disease as well as visits to the emergency room or a physician's office for the treatment of migraine will be summarized by treatment arm in terms of information reported at **Screening/Visit 1** compared to information reported at **EOs/Visit 2**. Concomitant medication use for migraine and/or pain and missed days of work and/or school will be summarized by treatment arm.

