### **10.9 Resource Utilization**

By-subject listings of any resource utilization will be listed and will be summarized using descriptive statistics, separated by treatment arm, and dose.

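### The SAP resource-use table omits physician's-office visits for migraine and the on-study period, both promised in the protocol, and neither change is declared (minor)

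*SAP*

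**What the plan says.** **Protocol.** The synopsis, under the resource-utilization criteria, lists "Any visits to an emergency room or physician's office for treatment of migraine in the 3 months prior to screening", to be compared with Visit 1 through Visit 2 and leaving out study-specific visits. The synopsis analysis text adds that "visits to the emergency room or a physician's office for the treatment of migraine will be summarized by treatment arm", setting what is reported at Visit 1 against what is reported at End of Study. Section 9.1.1.3 states for Visit 1 that "information regarding any ER visits or visit to physician's office for migraine treatment will be recorded", and that subjects are asked about resource use again at Visit 2. Section 10.9 is broad: "By-subject listings of any resource utilization will be listed and will be summarized using descriptive statistics". Section 5.3 makes on-study against pre-study resource use, including use for migraine, an additional objective to be explored.

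**SAP.** The endpoint in Section 3.5 is "Visits to an emergency room or urgent care for treatment of migraine", with no period given. The table in Section 13 reports "Counts and percentages of subjects with emergency room or urgent care visits for migraines in the last three months prior to Visit 1". For cardiovascular resource use the same section names two periods, the six months before Visit 1 and the time since Visit 1. It closes with "Additional information regarding these visits or changes will be presented in a listing". Section 5.1 sets out several departures from the protocol analysis; none concerns resource utilization.

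**The concern.** The protocol's migraine resource variable has two settings (emergency room, physician's office) and two periods (before the study, on study). The SAP changes the first dimension and drops half of the second, without saying so. Protocol Section 10 expects changes to the described analysis methods to be explained and justified in the SAP, so a reader of Section 5.1 would assume that this variable was analysed as the protocol describes.

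Two consequences follow if the SAP is carried out literally. A subject whose only migraine care was at a physician's office has no place in the table. And with no on-study migraine count, the comparison that the additional objective asks for cannot be read from the output. The second is the larger gap: restoring office visits to a pre-study row alone would still leave nothing to compare it with.

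**Working it through.** The documents give no figure to reproduce, so the check sets the texts side by side.

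1. **Setting of care.** Protocol synopsis (criteria and analysis text) and Section 9.1.1.3: emergency room or physician's office. SAP Sections 3.5 and 13: emergency room or urgent care. Neither document defines urgent care as including ordinary office visits.

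2. **Period.** Protocol synopsis: 3 months before screening against Visit 1 through Visit 2. SAP Section 13, migraine: three months before Visit 1 only. SAP Section 13, cardiovascular: before and since Visit 1. The sentence naming both periods refers to the six-month look-back, which belongs to the cardiovascular items. The migraine sentence comes after it and carries its own, single period.

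3. **Coverage.** 2 settings × 2 periods = 4 combinations in the protocol. The SAP table plainly covers 1 of the 4, emergency-room visits before Visit 1, and pools it with urgent care. It covers neither office combination explicitly, and it does not present emergency-room visits on study.

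4. **Could the listing fill the gap?** It is confined to the visits and changes already named in Section 13. Even if on-study emergency-room visits were listed, office visits would not be, and a listing is not the summary by arm that the protocol promises.

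5. **Are the data planned?** By the protocol, yes: the Schedule of Assessments has a resource-utilization review at Visit 1 and at End of Study, and Section 5.6.4 repeats the latter. The SAP table is on the Safety population, that is, subjects who took study drug. The reduced End of Study visit for subjects who treated no attack therefore does not explain the missing period.

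6. **Is the change declared?** SAP Section 5.1 covers second-dose populations, baseline significance tests, mild headaches, the Cochran-Mantel-Haenszel test, symptom-specific and time-to-event analyses of the most bothersome symptom, and subgroups. Resource utilization is not among them.

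**The case against.** The best defence is that little depends on this. The objective is exploratory, the output is counts and percentages, and each subject treats one attack within about 8 weeks. No hypothesis, alpha or power attaches to it. That stands, and it sets the severity.

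A second defence is that the CRF is not among the documents. The SAP wording may reflect the categories that were actually collected, with urgent care standing in for unscheduled office care. That is possible and affects the remedy, but it does not remove the inconsistency: the protocol says office visits are recorded, and a change of category would still need declaring.

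Three stronger readings are tempting, and the documents do not support them.

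- **That cardiovascular use is narrowed in the same way, because cardiovascular events have no row.** The protocol's own analysis text in the synopsis names cardiologist visits, procedures, hospitalizations and new or adjusted treatments, which is the list the SAP uses. Events appear in the objective and the collection items, but that analysis text promises no separate count of them. On-study events are also captured as adverse events (SAP Section 12.1), and earlier conditions as medical history (SAP Section 8.3).
- **That the share of care missed can be estimated.** There are no visit counts in either document. A share of visits would not convert to a share of subjects either: someone with both an office and an emergency-room visit is still counted, and the overlap between urgent care and office care is unknown.
- **That a treatment comparison is distorted.** The only migraine row planned describes the time before Visit 1, before randomized treatment. The defect is that the on-study comparison is absent, not that it is biased.

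**Conclusion.** The point holds as a minor, undeclared inconsistency between protocol and SAP. Followed as written, the SAP omits office-based migraine care from its resource table and cannot deliver the pre-study versus on-study migraine comparison in the additional objectives. Its extent is three of the protocol's four combinations of setting and period without a stated row; how many subjects that involves cannot be determined from the documents. No primary, key secondary or safety conclusion changes.

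This rests on two assumptions: that urgent care is not meant to include ordinary physician's-office visits, since no definition says so, and that the migraine sentence in SAP Section 13 is meant literally as to period. If the first fails, part of the pre-study office use is recovered. If the second fails, the on-study period is recovered. In either case the SAP text would still need to say so.

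**What to change.** In SAP Sections 3.5 and 13, define the migraine variable as emergency-room, urgent-care and physician's-office visits for treatment of migraine, excluding study visits. Give one row for each type and one for any visit. Present every row for both periods: the 3 months before Visit 1, and Visit 1 to End of Study. Extend the listing to the same visits.

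If the CRF did not collect office visits separately, state that in SAP Section 5.1 with the reason, and still add the on-study period for the categories that were collected.

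The cost is a few sentences of SAP text and a few table rows. No new data are needed if collection followed protocol Section 9.1.1.3; whether it did should be checked against the CRF first. The cardiovascular rows need no change on this account.
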